5.2 Pelvic Exam

Study examinations will take place in a private room equipped with a gynecologic exam bed in the FACES clinic. Participants will be placed in a dorsal lithotomy position. The external genitalia will be examined to look for any evidence of infection or genital ulcer disease. After introduction of a sterile speculum, the clinician will use a swab to wipe away cervical mucus or blood and assess for evidence of cervicitis.²⁶ In the case of concern for cervical infection, routine testing and treatment will be performed and screening deferred until treatment is complete.⁸

5.3 Visual Inspection with Acetic Acid

In this study, VIA will be performed on all HPV positive women to assess for eligibility for ablative treatment in a process referred to visual assessment for treatment (VAT).⁶ After identification of the cervical anatomy, including the squamocolumnar junction, the clinician will apply 5% acetic acid to the cervix. After one minute, the clinician will examine the cervix again to interpret results of the VIA according to the following criteria:

VIA will be defined as negative if the following findings are present:²⁶

1. Circumferential identification of the squamocolumnar junction (SCJ)
2. No aceto-white or faint, ill-defined white lesions at the SCJ or aceto-white lesions far away from the SCJ

VIA will be defined as positive if the following findings are present, as established by the International Agency for Research on Cancer (IARC):^{8,26}

1. Raised, thickened, a well-defined, opaque aceto-white lesion at or close to the SCJ
2. Large circumferential aceto-white lesions covering the external os
3. Pre-existing condyloma or leukoplakia which turns intensely white after application of acetic acid

The WHO criteria for cryotherapy will be used to assess for eligibility for thermal coagulation – namely, if the squamocolumnar junction is fully visualized, the cervical lesion covers less than 75% of the cervix, and there is no endocervical component or suspicion of cancer.⁴ These criteria for the use of thermal coagulation widely accepted and is used in other studies and clinical settings.

5.4 Baseline Colposcopy and Cervical Biopsy

All women with a positive HPV screening test will undergo a colposcopy exam followed by a directed biopsy of abnormal areas using a punch biopsy forceps. If there are no abnormal areas, a random biopsy will be performed at 6 or 12 O'clock. Colposcopy exam will be done in accordance with the International Federation for Cervical Pathology and Colposcopy (IFCPC) guidelines, including sequential evaluation using a green filter and acetic acid.²⁷ During the cervical biopsy, the study clinician will use a biopsy forceps to obtain a rice-grain-sized cervical specimen, either at the site of abnormality or at random quadrants. The specimen(s) will be placed in a container with formalin, labeled and stored while awaiting transportation to pathology.

5.5 Thermocoagulation

Treatment of positive screening results will be performed using the Liger Thermocoagulator device.²⁸ Eligibility for ablative treatment with the thermal coagulator is similar to the WHO-recommended criteria for cryotherapy, as described above.^{4,13} The Liger thermocoagulator device is a second-generation, hand-held, battery powered, rechargeable device that was developed by Liger Medical in Utah USA specifically for use in low resource settings. Previous generations of this device have been used for treatment of precancerous lesions in multiple studies both in Sub-Saharan Africa and in Europe.^{6,7,13,17,18,29}

The cordless, rechargeable device has two components, the detachable probe that comes in different sizes to match lesion size, and is heated once in contact with the cervix, and the hand-held portion that contains the battery and control mechanism with automated timing. Once activated, the tip of the probe, in contact with the cervix heats up to 100 °C over approximately four seconds. Once at this temperature, an inbuilt timer starts for a recommended treatment length of 20 seconds. If the lesion is larger than the probe, or the transformation zone is not fully covered by the probe, several overlapping applications are performed to cover the entire lesion.¹⁷

This temperature and length of treatment induce tissue necrosis to a depth of just over 5 mm, which is necessary to destroy close to 100% of CIN3 lesions.⁶ While there is no consensus in the literature about the optimal thermoablation temperature and application time, Prendiville *et al.* compared the depth of tissue damage produced by the Liger thermocoagulator applied for 20, 30, or 45 seconds at 90 °C, 100 °C, and 120 °C on a tissue model.³⁰ They found that a depth of more than 5 mm was achieved for all application durations at both 100 °C and 120 °C, supporting the choice of 100 °C for 20 seconds setting.³⁰

This setting has been used for treatment of precancerous lesions in many studies including a recent study in Brazil among women with biopsy-proven CIN2/3, in which 85% (17/20) of those with CIN2 and 84% (27/32) with CIN3 had no evidence of disease at 12-month follow-up.¹⁷ Studies on thermocoagulation so far confirm patient tolerability with no local anesthesia or analgesics, similar to cryotherapy.^{6,13,17,18,31}

Once treatment is complete, for sterilization, the manufacturer recommends one of two methods. The detachable probe can be rinsed with mild detergent and water, and then soaked for 20-60 minutes with ~ 2.5% glutaraldehyde solution (Cydex) or 0.5% Chlorine solution.²⁸ Alternatively, the probe can be decontaminated with alcohol and re-heated to 100 °C for sterilization before reuse, as viral proteins are denatured at temperatures above 60 °C.^{15,17,28}

5.6 Post-treatment Pain Assessment

Pain will be assessed using a visual analog scale (VAS) immediately following treatment.

5.7 4-6 Week Follow-up

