2.3 Secondary Objectives

To evaluate patient safety of thermal coagulation for the treatment of abnormal cervical lesions within a screen-and-treat program among HIV-positive women in Western Kenya.

- Endpoints:
 - Average pain score immediately after treatment
 - The rate of AEs reported at 4-6 week follow-up

To evaluate patient satisfaction with thermal coagulation for the treatment of abnormal cervical lesions within a screen-and-treat program among HIV-positive women in Western Kenya.

- Endpoint: Proportion of participants who answer 'yes' to satisfaction questions at 4-6 week follow-up.

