3.1 Characteristics

We will prospectively enroll four hundred HIV-positive women to undergo cervical cancer screening at FACES-supported MOH clinics in Kisumu County. After informed consent, clinical and demographic information will be collected, and participants will undergo cervical cancer screening using HPV testing. Women who previously screened positive for HPV (within the last 3 months) but have not undergone treatment will also be eligible for recruitment. Women with a positive HPV test will be evaluated for treatment with thermal coagulation, per WHO standards of ablative treatment. Per the WHO and Kenya Ministry of Health guidelines, women who will be candidates for thermal coagulation if the squamocolumnar junction is fully visualized, the cervical lesion covers less than 75% of the cervix, and there is no endocervical component or suspicion of cancer.⁸ Women who are not candidates for ablation will be referred to nearby a referral facility. All participants with a positive HPV test will undergo directed biopsy just prior to treatment for disease ascertainment but proceed to have same-day treatment, according to the WHO guidelines for screen & treat.

At 12-months after treatment, all participants treated at baseline will undergo repeat colposcopy, directed biopsy for those with cervical abnormalities or those with CIN2/3 at baseline, as well as provider collected HPV testing for persistence. Twenty-five percent of women with normal colposcopy will have a random biopsy at 6 or 12-O'Clock to confirm the absence of disease. Pain will be assessed immediately following treatment using a visual analog scale (VAS). The presence and severity of AEs will be assessed 4-6 weeks following treatment via a phone call, or in person visit, if warranted. Healthcare providers offering thermal ablation for the treatment of precancerous lesions will be surveyed at 4-6 week follow-up to evaluate provider acceptability and satisfaction with this treatment method.

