7.2 Secondary Objectives

To evaluate the safety of thermal coagulation for the treatment of abnormal cervical lesions within a screen-and-treat program among HIV-positive women in Western Kenya.

Statistical Analysis: We will calculate the average pain score immediately after treatment, as reported using the visual analog scale with confidence intervals. We will determine the proportion of women who experience grade 2 and 3 AEs, and severe adverse events (SAEs) during follow-up and calculate confidence intervals. Rates of AEs and SAEs will be compared to published rates for cryotherapy amongst this population (2.1% with mild pain or cramping, 1.6% with malodorous excessive vaginal discharge, 0.7% with mild bleeding or spotting, and no severe adverse events).¹² We will use one sample proportion test to compare proportions.

To evaluate patient satisfaction with thermal coagulation for the treatment of abnormal cervical lesions within a screen-and-treat program among HIV-positive women in Western Kenya.

Statistical Analysis: We will evaluate patient satisfaction with thermocoagulation by determining the proportion of participants answering yes to satisfaction questions at the 4-6 week follow-up.

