8.5.4 Management of Risks to Subjects

Expected AEs

Expected AEs associated with the Thermocoagulation include:

- Mild discomfort associated with biopsy collection and treatment
- Mild vaginal discharge for a few days to weeks following treatment

AE Management

- Concerning symptoms will be evaluated in person by a trained clinician, and treatment offered where appropriate
- AEs will be evaluated for whether or not they are attributable to the treatment and reported as such
- All AEs will be followed to conclusion

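### The single pain score follows both a punch biopsy and the ablation in every treated woman, so the secondary pain endpoint cannot isolate the pain of thermocoagulation

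*Combined protocol and SAP*

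**What the plan says.** All references are to the combined protocol and SAP.

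- **Timing of the score.** Section 5.6: "Pain will be assessed using a visual analog scale (VAS) immediately following treatment". Section 3.1 gives the same single time point. No score is planned before the examination, or between biopsy and ablation.
- **Order of procedures.** Section 3.1: "All participants with a positive HPV test will undergo directed biopsy just prior to treatment for disease ascertainment but proceed to have same-day treatment". Section 5.4 covers women with normal colposcopy: "If there are no abnormal areas, a random biopsy will be performed at 6 or 12 O'clock". Section 7.1 also puts biopsy before same-day treatment.
- **Endpoint.** Section 2.3 lists "Average pain score immediately after treatment" under the objective on the safety of thermal coagulation within a screen-and-treat programme.
- **Analysis.** Section 7.2: "We will calculate the average pain score immediately after treatment, as reported using the visual analog scale with confidence intervals". No change score, threshold, test or comparator is attached to the VAS.
- **Expected discomfort.** Section 3.5.1 accepts that colposcopy and biopsy may cause some discomfort and expects it to be minimal. Section 8.5.4 lists, as one expected adverse event of thermocoagulation, "Mild discomfort associated with biopsy collection and treatment".

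**The concern.** The endpoint belongs to an objective about one procedure, but the measurement follows two. Each woman rates her pain minutes after a punch biopsy and immediately after ablation, and section 3.5.1 notes that the ablation covers the biopsied tissue. No treated woman goes without a biopsy and there is no control arm, so no contrast in the data shows how much of the score is due to ablation.

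This matters for how the result is used. Sections 1.1 and 1.2 describe screen-and-treat as treatment without histological verification, and section 1.5 says the results are meant to inform national programmes and WHO guidance. A woman treated in such a programme would not have the biopsy. The reported mean describes a visit that the programme would not deliver, and a larger sample would only estimate that mixed quantity more tightly.

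**Working it through.** The plan states no pain figure, so there is none to reproduce. The check is whether ablation pain can be identified from the planned data.

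**Step 1. What the planned score contains.** For one woman let
- *D* = discomfort present before the procedures,
- *b1* = biopsy pain just before the probe is applied,
- *b2* = biopsy pain still felt immediately after ablation,
- *A* = pain added by ablation.

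Assume the parts add. The planned score is *Y* = *D* + *b2* + *A*. Sections 3.1 and 5.4 make biopsy universal, so the mean of *Y* is one observed quantity with three unknown parts. The mean of *A* is not identified, whatever the number of women.

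**Step 2. What bound the planned score gives.** Since *A* = *Y* − *D* − *b2*, and *D* and *b2* are not negative, *A* ≤ *Y*. The mean of *Y* is an upper bound for ablation pain. If *D* and *b2* are close to zero at the time of rating, the bound is close to *A* itself.

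**Step 3. What a second mark adds.** A mark after biopsy and before the probe gives *X* = *D* + *b1*. Then *Y* − *X* = *A* − (*b1* − *b2*).
- If biopsy pain does not change between the marks (*b1* = *b2*), the change equals *A*.
- If biopsy pain fades (*b2* < *b1*), the change understates *A*.

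So, with stable *D* and biopsy pain that does not rise between marks, mean(*Y* − *X*) ≤ mean(*A*) ≤ mean(*Y*). The width of this bracket is mean(*Y*) − mean(*Y* − *X*) = mean(*X*), the post-biopsy score. If biopsy discomfort is as slight as section 3.5.1 expects, the bracket will be narrow, and the data will show it.

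**Step 4. Precision, as an illustration only.** The documents give no VAS range or SD. Assume a 0–10 scale, SD 1.5 to 3.0, a correlation ρ of 0.3 to 0.7 between the two marks, and 400 treated women (section 7.1).

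| Quantity | Formula for 95% CI half-width | Lowest | Highest |
|---|---|---|---|
| Planned single mean | 1.96 × SD / √400 | 1.96 × 1.5 / 20 = 0.15 | 1.96 × 3.0 / 20 = 0.29 |
| Within-woman change | 1.96 × SD × √(2(1 − ρ)) / √400 | SD 1.5, ρ 0.7: 1.96 × 1.16 / 20 = 0.11 | SD 3.0, ρ 0.3: 1.96 × 3.55 / 20 = 0.35 |

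The number treated may be below 400. Section 3.1 enrols 400 women for screening and refers those unsuitable for ablation, whereas section 7.1 speaks of 400 HPV-positive women. With 200 treated (an assumption), each half-width grows by √2, to 0.21–0.42 for the single mean and 0.16–0.49 for the change. On these assumptions the change is estimated about as precisely as the planned mean, with no extra participants.

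**The case against.** The endpoint as worded is accurate. Sections 2.3 and 7.2 call it an average score after treatment and do not claim that it is due to ablation alone. It is a descriptive mean, and the comparison with published cryotherapy rates in section 7.2 concerns adverse events, not the VAS. **This stands.** A reader might infer that the protocol presents the score as the pain of ablation by itself; no section says so. What remains is that the parent objective concerns thermal coagulation and the plan does not state the limit on attribution.

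The upward direction is also not certain. It requires biopsy pain that lasts into a rating made after a later stimulus. If it does last, the error is conservative for a claim of tolerability. **This stands too**, which is why the score is described only as a rough upper bound.

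The VAS question and anchors are not in the protocol, and section 8.7 shows SOPs and a study manual as separate items. Wording directed at the ablation step would reduce the mixing. It would not reliably remove it, because the two steps are close in time and affect the same tissue. The adverse-event questionnaire at 4–6 weeks (section 5.7.1) does not help, because it grades later symptoms and not procedural pain by source.

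Finally, a change score is not pure ablation pain, and a mark between the steps interrupts the examination before the ablation that section 3.5.1 relies on to stop biopsy bleeding. **Both points are right.** The first is met by reporting both scores beside the change. The second is a real, small cost, and is why the mark should be taken only where it does not delay care.

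**Conclusion.** The point holds as a limit on attribution in a secondary, descriptive endpoint. The planned mean measures pain after biopsy plus thermocoagulation in all treated women, and the ablation part cannot be recovered from it at any sample size. That conclusion follows from the order of procedures and the single rating, and needs no assumed number. The upper-bound reading rests on additive pain and on biopsy pain still being felt at the time of rating.

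The size is unknown. A reader might infer that the score overstates ablation pain by a definite amount, or by some multiple of the confidence interval's half-width. The documents do not support that. They give no VAS range, mean or SD and no estimate of biopsy pain beyond the expectation that it is minimal or mild, so such a multiple would be one assumption divided by another.

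This is an inexpensive improvement, not a defect that undermines the trial.

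**What to change.** 1. In sections 3.1 and 5.6, add one VAS mark after the biopsy and before the probe is applied, where this does not delay care.
2. In section 7.2, report together, with confidence intervals, the post-biopsy score, the post-ablation score and the within-woman change. Describe the change as the increment after ablation, and state that it may understate ablation pain if biopsy pain fades between marks. Keep the planned post-ablation mean as the upper bound.
3. Whether or not the second mark is added, label the endpoint in sections 2.3 and 7.2 as *pain after biopsy plus thermocoagulation*.

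Cost: a brief pause during the examination and one extra CRF field. No further visit, staff or clinical procedure is needed. The relabelling alone costs nothing.

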5.7.1 Adverse Events Evaluation

Adverse events will be evaluated at 4-6 weeks following treatment with a follow-up phone call or in-person visit (based on patient preference, distance from the clinic, and symptom severity) at which time a woman's subjective assessment of symptoms and duration will be obtained and recorded in a study questionnaire. Adverse events will be graded using the Division of AIDS Table for Grading Severity of female genital symptoms in which Grade 0 is normal, 1 is mild, 2 is moderate and 3 is severe symptoms. Women who elect a phone-call evaluation and report grade 2 or 3 symptoms will be asked to present for an in-person evaluation. Transport reimbursement will be provided for all study visits.

5.7.2 Provider Acceptability Evaluation

At 4-6 week follow up, providers will be surveyed using a Provider Acceptability survey, modified from the System Usability Scale to evaluate provider acceptability and satisfaction with the use of thermal coagulation for treatment of precancerous lesions.³²

5.8 12 Month Follow-up Exam

At approximately 12-months after treatment, all participants treated at baseline will undergo repeat colposcopy, biopsy for those with CIN2/3 at baseline or those with suspicious lesions on colposcopy, as well as provider collected HPV-collection for persistence. Twenty-five percent of women with normal colposcopy will have a random biopsy at 6 or 12-O'Clock for ascertainment and avoidance of verification bias.

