6.1 Staff Training

Study exams will be carried out by clinical officers and nurses who have undergone training in HPV testing, speculum exam, VIA, specimen collection, colposcopy, and biopsy. The training will be based on the International Agency for Research on Cancer (IARC), Kenya Ministry of Health (MOH) and WHO curricula and will contain didactic lectures, discussions, review of cervical photographs, and hands-on experience.^{33,8,34,35}

Several providers at FACES have already undergone training for cervical cancer screening and treatment based on cryotherapy and thermocoagulation. Additional, specific training and demonstration regarding the use of the Liger thermocoagulator will be performed by the Principal Investigator, a U.S trained Gynecologist, using instructional material, including demonstration videos, from the manufacturer. All providers will be observed performing several treatment cases to ensure competency. All study staff will undergo training in Good Clinical Practices, informed consent, participant confidentiality, and study-specific procedures.

After satisfactory completion of training, including an examination and proctored procedures, staff will receive certification. Periodic training and assessment sessions will be done throughout the study. Lab technicians will be oriented in the proper handling, storage, and transport of laboratory specimens.

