7.1 Primary Objective

To evaluate the efficacy of thermal coagulation for the treatment of HIV-positive, HPV-positive women by assessing rates of HPV persistence and CIN2/3 at 12 months after treatment

Four hundred HIV-positive women with positive HPV testing will undergo colposcopy-directed biopsy for disease ascertainment prior to same-day treatment with thermal coagulation. At 12-months after treatment, all participants will undergo repeat HPV testing for persistence, and those who are HPV-positive will undergo repeat colposcopy, and biopsy as indicated for abnormal results, or random biopsy for 25% of those with normal colposcopy. We will define cure as a normal biopsy result or normal colposcopy among those who do not receive a biopsy.

Statistical Analysis: We will report the proportion of women with no evidence of cervical dysplasia at 12-months (primary outcome) follow-up, including 95% confidence intervals. We will extrapolate the rate of disease among those with normal colposcopy based on the rate of disease among the 25% in this group who will receive biopsy, and this will be incorporated in calculating persistence. We will perform a logistic regression to examine predictors of treatment success, using clinical and demographic variables as predictor variables. We will also report the rate of persistence of HPV at follow-up and compare with rates reported in the literature in this same population. We will compare efficacy rates for clearance of CIN2/3 to historical results following cryotherapy treatment in similar settings. A one-sample exact test will be used to compare the obtained efficacy proportion to that of historical controls.

We will leverage the robust infrastructure of the FACES in which patients are seen every one-to three months, and there is an established patient tracing system (including home visits) to reduce loss-to-follow-up. With a loss-to-follow-up rate of 10%, we will still be powered to answer this objective. Prior studies at this clinic have been able to achieve > 90% follow-up rate.³⁶ While limited by the lack of randomization to cryotherapy versus thermocoagulation, this study will provide pilot results that may enable a future randomized study evaluation of these two treatment methods.

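### No masking of the 12-month pathologist or colposcopist to baseline histology is specified, although the biopsy rule puts that result in the visit team's hands and cure is tested against a fixed historical boundary

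*Combined protocol and SAP*

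**What the plan says.** Section 7.1 sets the outcome: "We will define cure as a normal biopsy result or normal colposcopy among those who do not receive a biopsy". It compares clearance of CIN2/3 with historical cryotherapy results by a one-sample exact test and acknowledges the missing control: "While limited by the lack of randomization to cryotherapy versus thermocoagulation".

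Two sections agree on who is biopsied at 12 months. Section 5.8: "all participants treated at baseline will undergo repeat colposcopy, biopsy for those with CIN2/3 at baseline", and also for women whose colposcopy looks suspicious. Section 3.1: "directed biopsy for those with cervical abnormalities or those with CIN2/3 at baseline". Both add a random biopsy for a quarter of women with normal colposcopy, and 5.8 gives verification bias as the reason.

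Section 7.1 describes another pathway. After repeat HPV testing, "those who are HPV-positive will undergo repeat colposcopy, and biopsy as indicated for abnormal results, or random biopsy for 25% of those with normal colposcopy". Baseline CIN2/3 does not trigger a biopsy there.

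On the readers, section 6.1 says "Study exams will be carried out by clinical officers and nurses", after training. Section 5.4 says of the baseline specimens that they are "labeled and stored while awaiting transportation to pathology". The documents do not say who reads the histology, how many readers there are, or what the request form shows. Study-ID labelling appears in 6.2 as a rule for the database, not for readers.

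**The concern.** Colposcopic impression and histological grade both involve judgement. Followed as written, 5.8 requires the baseline grade to be at hand during the 12-month visit. Nothing says that the impression is recorded first, or that the grade is kept off the pathology request.

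In a randomised comparison with the same readers in both arms, a shared expectation would tend to cancel. Here the cure proportion is set against a fixed number, so any net shift enters the result in full. The reading of colposcopy as normal also decides who enters the group from which the 25% sample is drawn and to which its disease rate is extrapolated.

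At stake is whether a conclusion that few readings can turn might reflect what the readers knew about baseline disease.

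**Working it through.** **Inputs.** From 3.3: reference rate 77.2%, margin 10 points, 140 women with CIN2/3 (35% of 400), one-sided 0.025, stated power 90%, stated difference 0.0102. From 7.1: one-sample exact test. Boundary: 77.2% − 10% = 67.2%.

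**Step 1. The plan's own figure.** The exact rule at n = 140 is the smallest r with P(X ≥ r | p = 0.672) ≤ 0.025.
- r = 105: 0.0283, too large.
- r = 106: 0.0180, so at least 106 cures are needed.

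Power at a true 77.2% is P(X ≥ 106 | p = 0.772) = 70.3%. Adding the stated 0.0102 (p = 0.7822) gives 79.6%. The stated 90% is therefore not reproduced by the planned test at the stated alpha. That is a separate matter on which this point does not depend; 70.3% is used below as the reference power.

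**Step 2. Which reading decides cure.**

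| Group | Under 3.1 and 5.8 | Under 7.1 |
|---|---|---|
| Baseline CIN2/3 (non-inferiority set) | All biopsied; histology decides, colposcopy mainly affects the biopsy site | Colposcopy only if HPV-positive; biopsy if abnormal or in the 25% sample; colposcopy alone can decide |
| No baseline CIN2/3 | Biopsy if suspicious or in the 25% sample; otherwise colposcopy | Same as the row above |

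**Step 3. Share classified by colposcopy under 3.1 and 5.8.** Women without baseline CIN2/3: 1 − 0.35 = 0.65. Of those with normal colposcopy, 0.75 have no biopsy.
- Ceiling, all 65% normal: 0.65 × 0.75 = 48.8%.
- 70% normal (assumed): 0.488 × 0.7 = 34.1%.
- 90% normal (assumed): 0.488 × 0.9 = 43.9%.

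None of these women is in the non-inferiority set.

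**Step 4. Sensitivity of the test to a reading shift.** Let d be a net shift in the observed cure proportion in the CIN2/3 set. The values of d are assumptions.
- Upward: P(X ≥ 106 | p = 0.672 + d) is the chance of passing when the true rate is at the boundary.
- Downward: P(X ≥ 106 | p = 0.772 − d) is the power when the true rate is 77.2%.

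| d | Women of 140 | False-positive rate, upward | Power, downward |
|---|---|---|---|
| 0 | 0 | 1.8% | 70.3% |
| 1 point | 1.4 | 3.2% | 59.9% |
| 2 points | 2.8 | 5.5% | 48.9% |
| 3 points | 4.2 | 8.9% | 38.3% |
| 5 points | 7.0 | 20.3% | 20.3% |

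At n = 120, the plan's loss scenario, 92 cures are needed. Two points then move the false-positive rate from 1.5% to 4.5%, or power from 60.5% to 40.1%.

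**The case against.** **Silence is not unmasked reading.** A reader might infer that the readings will in fact be made with baseline results in view. The documents do not say so. The timetable in 8.7 lists SOPs and a study manual, which are not among the documents and may cover this. Nor does 6.1 say that the person who treated a woman examines her at 12 months; it describes a pool of trained staff. Both limits stand. What remains is that no masking is specified for the primary outcome and that 5.8 requires the baseline result to be available.

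**Colposcopy looks more important than it is.** It is tempting to say that about half of the women are judged on colposcopy alone and that this distorts the non-inferiority test. Under 3.1 and 5.8 it does not: the 49% is a ceiling and covers only women outside that comparison. Section 7.1 also partly corrects their classification by extrapolating from the 25% biopsied, though that sample addresses missed disease in unbiopsied women rather than reader expectation.

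**Size and direction are unknown.** Nothing in the documents supports a particular shift. Knowing of baseline CIN2/3 could prompt a closer search and lower the cure rate; knowing that the lesion was treated could raise it. A reader might infer an inflated cure rate; the documents do not support one direction over the other.

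**The remedy is partial.** Every woman seen at 12 months was treated, and hiding the baseline grade cannot hide that. Nor do the documents say how the readers of the historical cryotherapy study were informed, so the effect of masking on comparability with it cannot be judged. This stands and limits what the change can achieve.

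**Staffing is not described.** Someone must hold the baseline result until the impression is recorded. That is a matter of the order of forms and needs no second reader, but the clinics should confirm it is workable.

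**Conclusion.** The point holds as a cheap improvement, not as evidence of bias. No masking to baseline histology is specified for either 12-month reader, and the biopsy rule in 3.1 and 5.8 puts that result with the visit team. On that pathway the pathology reading matters most, because it decides cure in the CIN2/3 set. Colposcopy classifies an assumed 34–44% of treated women (at most 49%), all without baseline CIN2/3 and subject to the extrapolation from the biopsy sample. If 7.1 is the intended pathway, colposcopy could also decide cure within the CIN2/3 set, so the weight of each reading cannot be settled until the sections agree.

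The size is a sensitivity, not an estimate. It rests on 140 evaluable women, the 67.2% boundary, the exact test at one-sided 0.025 and an assumed net shift. Two points, about 3 women, would triple the false-positive rate (1.8% to 5.5%, above the nominal 2.5%) or take about 21 points off power (70% to 49%).

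**What to change.** First, reconcile 3.1 and 5.8 with 7.1 on who has colposcopy and biopsy at 12 months.

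Then add two rules to 5.8:
- Twelve-month specimens go to pathology under study ID, without baseline histology, HPV result or colposcopic impression. The grade is recorded before any of these is released for care.
- The examiner records the colposcopic impression before being told whether a biopsy is due, either for baseline CIN2/3 or for the 25% sample.

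The cost is a changed order on the visit form and a changed pathology request. The same examiners and pathologist can be used, with no additional biopsy and no change to sample size, alpha or treatment. The small downside is that the first pathology read lacks clinical history, which is released once the grade is recorded. The report should still state that the readers knew all women had been treated and that the comparison is historical.
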